3.2.2 Treatment period

The treatment period starts from randomization, and the investigational drug must be given within 3 days after randomization.

A cycle is defined as 6 weeks. SHR-1210 3 mg/kg will be given i.v. drip over half an hour, no less than 20 minutes and no more than 60 minutes, including rinsing period, on D1, D15 and D29 of each cycle in Group A, and on D1 and D22 of each cycle in Group B. Physical examination and laboratory examinations will be conducted during treatment, AE and concomitant medications information will be collected.

The following evaluation will be completed within 72 hours prior to each administration of investigational drug in each cycle of therapy:

ECOG PS, physical examination (at least including heart, lungs, abdomen, skin), vital signs, hematology, urinalysis, blood biochemistry, and blood electrolytes examination. The investigational drug can be given only after investigators have reviewed the laboratory test results.

Since the second treatment cycles, the following assessment will be completed at D1 of each cycle:

Coagulation function, alpha fetoprotein, thyroid function (TSH, FT3, FT4), virology (HBV markers or HCV markers), and Child-Pugh class.

In accordance with RECIST v1.1, the initial tumor imaging evaluation is assessed at 8 weeks (± 7 days), and then every 6 weeks (± 7 days), with or without dosing. After 12 months of dosing (i.e., the first dose), if tumor assessment is still required, it should be performed every 12 weeks (± 14 days) until the disease progresses or end of the study (whichever happens later).

The subjects who are evaluated as progressive disease can continue to receive treatment if they meet the criteria defined in Section 3.2.4.

The treatment period will end and proceed to follow-up period when the subjects terminate the study (see Section 5.5).

Note: the specific study procedures during the treatment period are shown in the study flowcharts.

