5.1.3. Derived variables

SHR-1210-Q2W group:

Duration of exposure (days) = date of last dose + 14 – date of first dose + 1

Duration of exposure (months) = (date of last dose +14 – date of first dose + 1) / 30.4375

Planned number of dosing = duration of drug exposure (days) / 14

Planned total dose (mg) = weight at baseline (kg) × 3 mg/kg × planned number of dosing

SHR-1210-Q3W group:

Duration of exposure (days) = date of last dose +21 – date of first dose + 1.

Duration of exposure (months) = (date of last dose +21 – date of first dose + 1) / 30.44.

Planned number of dosing = duration of drug exposure (day) / 21

Planned total dose (mg) = weight at baseline (kg) × 3 mg/kg × planned number of dosing

Cumulative dose (mg) = total dose during drug exposure

Dose intensity (mg/month) = cumulative dose/duration of drug exposure (months)

Compliance (%) = (cumulative dose/planned total dose) × 100%

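### SAP 5.1.3 carries the +1 of the exposure duration into the planned number of doses, so compliance and dose intensity come out slightly too low

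*SAP*

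**What the plan says.** SAP 5.1.3 (Derived variables) defines the duration of exposure separately by arm:

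- Q2W: "Duration of exposure (days) = date of last dose + 14 – date of first dose + 1"
- Q3W: "Duration of exposure (days) = date of last dose +21 – date of first dose + 1"

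The planned number of doses is this duration divided by the interval: "Planned number of dosing = duration of drug exposure (days) / 14" and "Planned number of dosing = duration of drug exposure (day) / 21". No rounding rule is given. The planned total dose follows as "Planned total dose (mg) = weight at baseline (kg) × 3 mg/kg × planned number of dosing", and the compliance rate as "Compliance (%) = (cumulative dose/planned total dose) × 100" percent. Dose intensity is cumulative dose divided by the same duration in months. The month divisor is 30.4375 in the Q2W arm and 30.44 in the Q3W arm.

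Protocol 3.2.2 gives the dosing days in a 42-day cycle: "on D1, D15 and D29 of each cycle in Group A, and on D1 and D22 of each cycle in Group B". SAP 5.2.5 counts a compliance rate below 50% among the critical or major protocol deviations.

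**The concern.** A compliance rate should be 100% for a subject who received every dose in full on the scheduled day. Under these formulas it is not, because the denominator contains a fraction of a dose that was never planned. Adding 14 or 21 days to the last dose reaches the date on which the next dose would fall due. The +1 then counts that date too, although it belongs to the next interval.

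Three outputs are exposed: the compliance rate, dose intensity, and the deviation flag at 50%. Deviations judged to have an important effect on the results can lead to exclusion from the per-protocol set (SAP 5.1.1). That set supports ORR, DCR and the OS rates. The SAP reports percentages to two decimals (5.1.2), so the error would be visible in print.

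**Working it through.** The documents give no numerical result here, so there is no figure to reproduce. The check applies the SAP formulas directly.

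**Inputs.** Interval k = 14 (Q2W) or 21 (Q3W), from Protocol 3.2.2 and SAP 5.1.3. Assumptions: full doses, weight unchanged from baseline, planned number not rounded.

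**On-schedule dosing.** For n doses exactly k days apart:

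- last − first = k(n − 1)
- SAP duration = k(n − 1) + k + 1 = kn + 1
- planned doses = (kn + 1)/k = n + 1/k
- compliance = n/(n + 1/k) = kn/(kn + 1)

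| Doses n | Q2W planned | Q2W compliance | Q3W planned | Q3W compliance |
|---|---|---|---|---|
| 1 | 1.0714 | 93.33% | 1.0476 | 95.45% |
| 2 | 2.0714 | 96.55% | 2.0476 | 97.67% |
| 4 | 4.0714 | 98.25% | 4.0476 | 98.82% |
| 8 | 8.0714 | 99.12% | 8.0476 | 99.41% |
| 10 | 10.0714 | 99.29% | 10.0476 | 99.53% |

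The shortfall is 1/(kn + 1). In Q2W it is 1/99 = 1.01% at 7 doses and 1/113 = 0.88% at 8. In Q3W it is 1/85 = 1.18% at 4 doses and 1/106 = 0.94% at 5.

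**Any dosing pattern.** Let D = last − first + k. The SAP uses D + 1 where D is needed, so compliance and dose intensity are both multiplied by D/(D + 1), whatever the adherence.

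**Which term is at fault.** Dropping only the +1 gives planned doses = n and compliance = 100.00% for every n in both arms. Dropping the interval and keeping the +1 gives, at n = 10 in Q2W, (126 + 1)/14 = 9.071 planned doses and 110.2% compliance. The interval must stay.

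**Comparison of the arms.** One completed cycle is 3 × 14 = 2 × 21 = 42 days, so both arms give 42/43 = 97.67%. Two cycles give 84/85 = 98.82% in both, and four give 168/169 = 99.41% in both.

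**The 50% limit.** Protocol 7.2.3 allows a delay of up to 6 weeks counted from the last dose. Take a Q2W subject with two full doses 42 days apart and none after:

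- without the +1: D = 42 + 14 = 56, planned = 4, compliance = 2/4 = 50.00%, not flagged
- with the +1: 57/14 = 4.07 planned, compliance = 28/57 = 49.12%, flagged

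The same spacing in Q3W gives 42/63 = 66.67% without the +1 and 42/64 = 65.63% with it, so there is no flag either way.

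**Month divisors.** (30.44 − 30.4375)/30.44 is about 0.008%, which has no practical effect.

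**The case against.** The best defence is that +1 is an ordinary inclusive day count. SAP 5.1.2 uses it for study days, and one extra day in a reported duration is about 0.03 month. As a convention for reporting duration, that stands. It fails once the same number is divided by 14 or 21 to count doses, because the interval already covers the days after the last dose.

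A second defence is rounding. If the planned number were rounded down or to the nearest whole dose, on-schedule compliance would be exactly 100%. The SAP states no such rule, and rounding would not repair dose intensity, which uses the duration directly. The percentages above do depend on no rounding.

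Several stronger readings are tempting but are not supported:

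- **That adding the interval is itself an error.** It is needed for n doses to span n intervals. The whole excess comes from the +1.
- **That the formula biases one arm against the other.** The arms differ at equal dose counts, for example 6.67 against 4.55 points short after one dose. At equal dose counts the Q2W subject has covered fewer days. After equal completed cycles the shortfall is identical.
- **That a compliant subject can never reach 100%.** This holds for exact intervals only. Protocol 6.5 allows intervals down to 12 and 18 days. Two Q2W doses 13 days apart give (13 + 14 + 1)/14 = 2 planned doses and 100%; ten such doses give 10/(132/14) = 106.06%. These values are still lowered by D/(D + 1).
- **That every exposure summary is wrong.** Of the items in SAP 5.5.1, duration and dose intensity use the formula. Cumulative dose does not, nor does the number of doses if that means doses given.
- **That the effect is too small ever to matter at the 50% limit.** The 42-day example shows otherwise, though it is a knife-edge case.

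**Conclusion.** Wrong as written, and minor. The extra day should not enter the planned number of doses. For a subject dosed exactly on schedule, with full doses at baseline weight and no rounding, compliance is understated by at most 6.67 points (Q2W) or 4.55 points (Q3W), at one dose. The algebra is exact under those assumptions. If doses follow current rather than baseline weight, which the documents do not settle, the ratio moves for that reason as well.

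The only consequence beyond a slightly low number is at the 50% deviation limit. There a rare subject could be listed as a major deviation because of the extra day alone. Exclusion from the per-protocol set would not follow automatically, since SAP 5.1.1 leaves that to judgement. No efficacy estimate on the full analysis set uses these variables, and membership of that set and of the safety set does not depend on them.

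**What to change.** In SAP 5.1.3, keep the added interval and drop the +1:

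- Q2W: planned number of doses = (last dose − first dose + 14)/14
- Q3W: planned number of doses = (last dose − first dose + 21)/21

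Use the same duration (last − first + 14 or + 21) for dose intensity. If an inclusive day count is wanted for the reported duration, define it as a separate variable that does not feed the planned doses or the intensity. State whether the planned number is kept as a fraction. Use one month divisor in both arms.

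The cost is a one-line formula change per arm in the SAP and the matching edit in the derivation program. No additional data are needed.

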5.1.4. Covariates and subgroups

This study will include the following subgroups:

- Gender (male vs. female)
- Age (< 65 vs. ≥ 65 years)
- Use of local therapy (yes/no)
- ECOG PS (0 points vs. 1 point): grouped by baseline ECOG PS
- Weight (< 60 kg vs. ≥ 60 kg vs. ≤ 55 kg vs. 55–70 kg vs. ≥ 70 kg)
- Baseline AFP level (< 200 ng/mL vs. ≥ 200 ng/mL, < 400 ng/mL vs. ≥ 400 ng/mL)
- Etiology (hepatitis B vs. non-hepatitis B): hepatitis B can be determined when the surface antigen or HBV-DNA is positive at baseline or HBV-DNA can be detected.
- BCLC stage (stage B vs. stage C)
- New anti-cancer therapy (yes vs. no): whether received other anti-cancer therapies during survival follow-up period.

Sub-populations will be classified in accordance with the type of previous therapy and number of treatment lines:

- Subgroup A: subjects previously treated with at least one standard treatment (sorafenib or oxaliplatin-based chemotherapy)
- Subgroup B: subjects previously treated with sorafenib
- Subgroup C: subjects treated with sorafenib only
- Subgroup D: subjects previously treated with only one standard treatment
- Subgroup E: subjects previously treated with two or more lines of treatment

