Tumor imaging evaluation	√	√	√	If the subject has no progression of disease when withdrawal from the study, the tumor still has to be evaluated once every 6 weeks according to RECIST v1.1, until progression of disease or start of subsequent anti-cancer therapy. Including the enhanced CT scan at thorax, abdomen, pelvis and site of lesions. In case of allergy to the contrast agent for enhanced CT scan, thoracic plain CT scan + abdominal and pelvic MRI can be performed. Bone scan is only performed when clinically indicated.

Items	End-of-Treatment ^[5]	Follow-up period		Comment
		Safety follow-up ^[6]	Survival follow-up ^[7]	
Others				
Survival information		√	√	
Subsequent anti-cancer therapy		√	√	

Note: [1] All the baseline data will be based on the value closest to the study dose.

- [2] For the subjects who have failed screening and are enrolled during re-screening period, if the visit procedures completed at the initial screening, and meet the required time limit for this procedure prior to start dose of the investigational drug and meet the inclusion criteria, they do not need to repeat the procedure during the re-screening period.
- [3] There's no ± 3 days window period for Day 1 of Cycle 1.
- [4] Starting from Cycle 2, the test will be performed on $D1 \pm 3$ of each cycle or at least once every 42 days, and more frequently when clinically indicated.
- [5] End of Study Treatment/Withdrawal from Study: If these tests/procedures have been completed within 7 days after withdrawal from the study, no further repetition is required.
- [6] Safety follow-up: until 90 days after last dose. During this period, one visit will be performed once every 30 days (± 7 days). The first (30 days after the last dose) and third (90 days after the last dose) safety visit after receiving drugs must be performed at the study center, the second visit (60 days after the last dose) is telephone visit, and only survival data, concomitant medication/therapy, AE need to be collected.
- [7] Survival follow-up: The subjects will enter the survival follow-up period after the end of safety follow-up period. During this period, the subjects will be followed up by telephone once every 30 days (± 7 days) for collection of survival data and subsequent therapies.

ABBREVIATIONS AND DEFINITIONS

The following abbreviations and special terms will be used in the study protocol.

Abbreviation and specific terms	Definition
AE	Adverse event
AFP	Alpha fetoprotein
ALP	Alkaline phosphatase

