3. STATISTICAL HYPOTHESIS

All analyses will be primarily based on descriptive statistical summary by group and overall. No formal statistical hypothesis testing will be performed. The overall 95% CIs of the two primary study endpoints, ORR and 6-month OS rate, will be calculated. The lower limit of the overall 95% CI of ORR is > 7% and the lower limit of the overall 95% CI of 6-month OS rate is >70% indicate that the drug is effective.

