4.1.6. Overall survival (OS)

Defined as the period from first dose to death due to any reason. It will be censored if no death occurs.

Rules for OS censoring are as below:

- If death is not obtained, the date of censoring will be the date of the last follow-up who are known to be alive.
- If the subject withdraws from the study and the date of death is not obtained, the date of censoring will be the last date who are known to be alive.

4.1.7. 6/9/12-month overall survival rate

Defined as the survival rate at 6/9/12 months after the date of first dose, which will be based on the Kaplan-Meier estimate.

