5.4.2. Subgroup analysis

Based on the FAS, subgroup analysis will be conducted merely on OS. The median OS and their 95% CIs will be provided for each subgroup. Forest plot will be prepared when necessary. The definition of subgroup is presented in section 5.1.4.

Based on the FAS, relevant efficacy endpoint analyses will be performed for sub-populations A, B, C, D, and E, with the same analytical method as above. The objective response swimmer plot and survival curves will be plotted for each sub-population.

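### The OS subgroup split by later anti-cancer therapy is fixed after baseline, so its 'yes' level carries guaranteed survival time

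*SAP*

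**What the plan says.** - **The factor.** SAP 5.1.4 lists "New anti-cancer therapy (yes vs. no): whether received other anti-cancer therapies during survival follow-up period" together with factors such as "ECOG PS (0 points vs. 1 point): grouped by baseline ECOG PS".
- **The output.** SAP 5.4.2 restricts these subgroup analyses to OS in the FAS: "The median OS and their 95% CIs will be provided for each subgroup. Forest plot will be prepared when necessary".
- **The clock.** SAP 4.1.6 on OS: "Defined as the period from first dose to death due to any reason".
- **The follow-up periods.** Protocol Study Procedures, note 6: "Safety follow-up: until 90 days after last dose". Note 7: "The subjects will enter the survival follow-up period after the end of safety follow-up period". Protocol 3.2.3 gives the same order.
- **Data collection.** The follow-up schedule in Study Procedures has a row for "subsequent anti-cancer therapy" ticked under both safety and survival follow-up.
- **Status of the analysis.** SAP section 3: "No formal statistical hypothesis testing will be performed". The success rule there uses only the overall ORR and the overall 6-month OS rate.

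Neither document gives a landmark, a time-dependent method or a caution for this factor.

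**The concern.** A subgroup for a time-to-event endpoint should be defined by what is known at time zero. Here time zero is the first dose, and the grouping depends on what happens months later. A subject can be 'yes' only by living through all study treatment, then the safety follow-up, then any wait for the new therapy. That time is counted as OS in the 'yes' group although death in it was impossible by definition. Subjects who die earlier are all placed in 'no'.

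There is a second problem on the literal wording: a subject whose new therapy falls wholly within the 90 days after last dose is counted as 'no', although the protocol collects that therapy.

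What is at stake is a misleading OS row. Shown next to baseline factors, it invites the reading that later therapy prolongs survival, when some or all of the difference may come from the definition.

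**Working it through.** **1. The plan's survival assumption.** SAP 2.3 plans on 80% alive at 6 months against 70%, one-sided 0.025, 90% power, n = 200.

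n = [(1.960·√(0.7·0.3) + 1.282·√(0.8·0.2)) / 0.10]² = 199.03, so 200. The exact binomial rule (at least 153 of 200 alive) has power 0.906 and alpha 0.0249. The stated figure is reproduced, and 200 × 1.1 = 220. No figure is stated for this subgroup; 80% and 70% are used below as survival inputs.

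**2. What the definition alone forces.** The earliest possible 'yes' is first dose + 90 days, about month 3. Assume a constant death hazard:

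- At 80%: λ = −ln(0.80)/6 = 0.0372 per month, median OS = ln 2/λ = 18.6 months. Deaths by month 3 = 1 − 0.80^0.5 = 10.6%, or 0.106 × 220 ≈ 23 subjects, all 'no'.
- At 70%: λ = 0.0594, median OS 11.7 months. Deaths by month 3 = 1 − 0.70^0.5 = 16.3%, about 36 of 220, all 'no'.

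Under a constant hazard and a therapy with no effect, a subject who starts it at month s has median OS s + 18.6 months. For 2 months of treatment, a 3-month gate and a 1-month wait, s = 6 and the median is 24.6 months instead of 18.6. At 70% it is 17.7 instead of 11.7.

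**3. Simulation with no true effect.** Time on treatment, uptake, waiting time and follow-up are not in the documents, so all are assumed. There were 200,000 subjects per scenario, with exponential treatment time and uniform follow-up of 12-24 or 8-23 months.

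- *Main range* (48 scenarios): 6-month OS 70% or 80%, median treatment 2-4 months, 30-60% willing to take new therapy, mean wait 1-2 months.
- *Stress case* (96 scenarios): median treatment 6-10 months, death hazard 4-8 times higher after stopping. Subjects still on study drug at the cut-off are then long-surviving 'no' subjects, which pulls the other way.

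| Apparent HR, 'yes' vs 'no' (true value 1) | Literal reading | Any therapy after last dose |
|---|---|---|
| Main range | 0.31-0.51 | 0.42-0.68 |
| Stress case | 0.52-0.90 | 0.72-1.30; medians reversed in 24 of 96 |

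The HR is not a planned output of SAP 5.4.2 and is used here only as a gauge. The planned output, literal reading, main range:

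- Median OS 18-20 ('yes') vs 7-10 months ('no') at 70%; not reached vs 11-16 months at 80%.
- 6-month OS 95-99% vs 53-76%.
- At n = 220 (2,000 null trials per setting, log-log CIs), the two 95% CIs for median OS fail to overlap in 17% to over 99% of trials across six main settings, and in 13-25% in two stress settings.

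If new therapy may start straight after the last dose with a mean wait of 1-2 months, 80-96% of those treated start inside the safety follow-up. The literal wording would then misplace subjects whose therapy also ends there.

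**4. A second set of assumptions.** At 80% 6-month OS, median treatment 2, 4 or 6 months, 50% or 80% uptake and a fixed cut-off at 12, 18 or 36 months, the crude death-rate ratio was 0.21-0.59 (literal) and 0.34-0.73 (any therapy). With new therapy as a time-dependent status it was 0.99-1.01. When 20% of subjects had long treatment and a low hazard, the crude literal ratio was still 0.33-0.74.

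**5. Does the remedy work under a true null?**

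- Time-dependent Cox from first dose: 0.98-1.02 (main), but 1.56-4.16 (stress).
- Time-dependent Cox from last dose: 0.98-1.02 in both.
- From last dose, if half the subjects have 2-3 times the hazard and lower uptake (20-30% vs 60%): 0.64-0.86. This is confounding by indication, which the method does not remove.

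**The case against.** **The 90-day gate is one reading.** Protocol 3.2.3 has survival follow-up collect other tumour treatment given since study treatment ended, with no 90-day exclusion, and the schedule also collects it during safety follow-up. The SAP could mean any later therapy. This is a fair reading. It removes the gate but not the guaranteed time up to the start of therapy: the main-range HR is still 0.42-0.68.

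**Size and direction are not established.** This stands. Subjects still on study drug at the cut-off are 'no', and the any-therapy stress case runs from 0.72 to 1.30. Confidence attaches to the structural flaw, not to a particular size. A row whose direction depends on unknown inputs is not interpretable either.

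**The weight is small.** There is no formal test, the forest plot is optional, and no claim for SHR-1210 is inflated. All true, and it caps the importance. But medians with CIs are what readers compare.

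**The list is not purely baseline.** The local-therapy factor in SAP 5.1.4 is not explicitly tied to baseline either. That is a fair point about the list and no defence of this factor.

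**A footnote would do.** It would lower the risk of misreading but leave the biased medians in the table.

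**Therapy dates may be incomplete.** The PFS rule in SAP 4.1.4 needs a start date only when no progression or death came first. Later starts are learned by monthly telephone contact, and the partial-date rules in SAP 5.1.6 cover safety data. This bears on the cost of the optional analysis, not on deletion.

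**Conclusion.** The concern holds. Following the SAP as written gives an OS comparison with built-in guaranteed time under either reading of the factor; this follows from the definitions and needs no assumption. The size does rest on assumptions. With short to moderate treatment, the median OS gap is about two-fold at 70% 6-month survival when later therapy does nothing. With long treatment and a sharp rise in mortality after stopping, the gap shrinks and can reverse if all later therapy is counted. The harm is confined to one descriptive OS subgroup. ORR, the overall 6-month OS rate and the success rule are unaffected. The SAP should be changed, but the trial's main conclusions do not depend on it.

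**What to change.** Delete the new anti-cancer therapy bullet from SAP 5.1.4, so that it enters neither the OS subgroup table nor a forest plot. Uptake of later therapy can still be tabulated descriptively. The cost is one bullet and one subgroup row; conduct, sample size and primary analyses do not change.

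If the sponsor wants the question kept:

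- Restrict it to subjects who have stopped study drug, with time zero at the last dose.
- Treat new therapy as a time-dependent covariate, or use a pre-specified landmark counted from the last dose. Do not start the time-dependent model at first dose.
- Count every new therapy begun after the last dose, including during safety follow-up.
- State that the result is non-causal, because confounding by indication remains.

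This option needs a start date for every new therapy, including therapy begun after progression, and a rule for partial dates. It also has a smaller sample, since subjects who die on study drug or are still receiving it do not contribute.
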